The masked and unmasked Study Coordinators will be responsible for scheduling all study visits taking utmost care to preserve the masking. Prior to randomizing the participant, the masked Coordinator will schedule the Treatment 1 and Treatment 2 study visits working under the pretense that both procedures involve stem cell therapy. Once the participant is randomized, the unmasked Study Coordinator will provide both the study hematologist and the GMP laboratory with information regarding which Treatment study visit will require bone marrow/cellular therapy and which will require sham aspiration/sham injection. The unmasked Study Coordinator will also schedule the post Treatment Day 1 and Week 1 study visits for both Study Periods.

The photographers and technicians obtaining OCT, perimetry and electroretinography (ERG) will be masked to the participants' treatment assignment to avoid bias in outcome assessment. The advanced retinal imaging team (described in Section 6.1.5), however, will be unmasked for the duration of the study.

At the time of informed consent and enrollment into the study and at the beginning of every study visit thereafter, participants will be reminded not to discuss details of the study procedures or their impressions of which injection they received with any member of the study team to preserve masking of the study team (i.e., investigators, technicians.)

Randomized Treatment Assignment								
Study Roles	Masked Status							
Principal Investigator	Masked							
Examining Ophthalmologist	Masked							
Masked Study Coordinator	Masked							
Hematologist	Unmasked							
Visual Acuity Examiner	Masked							
Treating Ophthalmologist	Unmasked							
Unmasked Study Coordinator	Unmasked							
Photographers	Masked							
OCT Technicians	Masked							
Perimetry Technicians	Masked							
ERG Technicians	Masked							
Study Participants	Masked							
Advanced Retinal Imaging Team	Unmasked							
GMP Laboratory Team	Unmasked							

TABLE 1: Enrollment Center Personnel – Masking for

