Once the participant qualifies for the study, the participant will be randomized 1:1 to either of the following study treatments: immediate cell therapy/deferred sham therapy or immediate sham therapy/deferred cellular therapy, where cell therapy consists of bone marrow aspiration and intravitreal injection of isolated CD34+ cells and sham therapy consists of sham bone marrow aspiration and sham injection. Immediate therapy refers to procedure administered at baseline while deferred therapy refers to procedure administered at month 6 of the study. The following assessments will be completed prior to study treatment that occurs on Day 0 and may be performed before or after randomization depending on the clinic or participant scheduling needs: autofluorescence, full field and multifocal electroretinography (ERG) and quality of life questionnaire. Additional imaging using a research-grade ultra-high-resolution OCT/OCTA and adaptive optics-OCT instruments will also be performed on a select subgroup of participants who qualify and consent.

Prior to randomization, the participant will meet with the study hematologist to review the aspiration procedure. The hematologist will review the participant's medical history, concomitant medications and blood work (including CBC) to ensure that the participant is a good candidate for a bone marrow aspiration. Any abnormal lab work and review of systems will be reviewed by the hematologist to determine whether it would impact the outcome of the bone marrow aspiration procedure and continued enrollment in the study.

Using the DCC's electronic data capture (EDC) system, Advantage eClinical[®], the unmasked Study Coordinator will randomize the participant, and will disseminate this information in a confidential manner to the hematologist and GMP laboratory as described in section 6.1.2.

On the morning of the study procedure, the participant will meet with the hematologist and the unmasked study coordinator to ensure there are no new contraindications to proceeding with study treatment that day.

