the CD34+ cells from the mononuclear cell fraction. There will be no genetic research testing performed. The isolated CD34+ cells will be washed, subjected to stat sterility assays (including endotoxin assay and gram stain), and stat viability testing with trypan blue staining and resuspended in 0.15 cc volume of BSS Plus. The final stem cell product (0.1 cc containing at least 800,000 viable nucleated CD34+ cells (where the cell count is based on the Miltenyi CliniMACS cell sorting process as noted above) will be sent to the Eye Center in a 1 ml tuberculin syringe for intravitreal injection. The remaining 0.05 cc of the final stem cell product will be used for post-release analysis to characterize the final stem cell product. This will include flow cytometry for CD34 and CD3 content and 7-AAD viability testing. Additional analysis for potency and characterization of the final product will be performed. These additional analyses will include flow cytometric panel analysis for hematopoietic stem cells that are CD133(+)/CD45(+)/CD34(+) versus angiogenic cells (i.e., endothelial progenitor cells) that are CD31(+)/VEGFR-2(+)/CD45(-)/CD34(+). In addition, the post release flow cytometry panel will include analysis of CD34+ cells with VEGF receptor-2 (VEGFR-2), namely VEGFR-2+/CD34+, as well as, % CD133(+); % CD31(+); % CD45(+); % VEGFR-2 (+).

On the morning of the study procedure, ETDRS VA is performed prior to the aspiration procedure and study injection. In addition, the unmasked treating ophthalmologist will perform a complete eye exam including fundus examination and a slit lamp examination of the study eye to ensure there are no new changes from baseline. This is done prior to study injection. The isolated CD34+ cells will be injected intravitreally by the unmasked treating ophthalmologist (retinal specialist) under local anesthesia. The intravitreal injection will be performed within two hours and on the same day following release of the final stem cell product from the GMP laboratory.

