The participants will have a complete eye examination 1 day and 1 week (±2 days) after their first study treatment (either cell or sham) by the unmasked treating ophthalmologist. Thereafter, a follow-up examination 1 month (±7 days), 3 months (±14 days) and 6 months (±30 days) will be conducted by the masked examining ophthalmologist. At month 6, the participant will receive the second study treatment (either cellular or sham therapy which is the opposite of what they originally received) by the unmasked treating ophthalmologist. Prior to the receipt of the second study treatment, the participant will meet with the study hematologist to review the aspiration procedure. Similar to the first consult, the hematologist will review the participant's medical history, concomitant medications, and blood work (including CBC) to ensure that the participant is still a good candidate for bone marrow aspiration. Any abnormal lab work and review of systems will be reviewed by the hematologist to determine whether it would impact the outcome of the bone marrow aspiration procedure and continued treatment in the study. In addition, females of child-bearing potential must have a negative pregnancy test within 2 weeks of the second study treatment. Similar to what occurs for the first treatment, the study team will meet with the participant on the morning of the study procedure to ensure there are no new contraindications to proceeding with study treatment that day.

Following the study injection, the unmasked treating ophthalmologist will conduct a follow-up exam 1 day and 1 week after this second study treatment. The masked examining ophthalmologist will conduct an exam 1 month, 3 months (\pm 14 days) and 6 months (\pm 30 days) after the second study treatment (i.e., at approximately 7, 9 and 12 months after the first study treatment).

The bone marrow aspiration wound site will be inspected visually for infection at the 1 day and 1 week (±2 days) post-procedure examinations by the unmasked treating ophthalmologist.

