3.3 Randomization

Randomization will occur after informed consent has been obtained and once a participant is confirmed to be eligible. Randomization will need to occur prior to the baseline visit for logistical and scheduling reasons. Much coordination among the hematologist, the Good Manufacturing Practices (GMP) facility, and the treating ophthalmologist needs to occur on days in which the cellular therapy is given. Therefore, knowing which treatment arm to which the participant has been randomized prior to the baseline visit is necessary. Great care will be taken to choose participants who are highly motivated to participate so as to prevent drop-out post-randomization.

A secure, internet-based eligibility, enrollment, and randomization system is integrated into the study to control and document the randomization assignments. Eligible participants will be randomized in a 1:1 ratio to immediate cellular therapy/deferred sham therapy or immediate

sham/deferred cellular therapy. Random assignments are generated and maintained by the Data Coordinating Center (DCC).

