4.1.2 Intent-to-Treat Population

The (modified) intent-to-treat population consists of all participants who were randomized and received the first injection (cellular or sham). For analyses, these participants will be analyzed in the arm to which they were randomized.

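### At Treatment 1, staff who know the arm decide whether a participant proceeds, and anyone never injected leaves the modified ITT set, so exclusion after randomization can depend on arm

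*Protocol*

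**What the plan says.** **Who learns the arm, and when.** Protocol 6.1.5: "the unmasked Study Coordinator will randomize the participant, and will disseminate this information in a confidential manner to the hematologist and GMP laboratory". Protocol 6.1.2 adds that "the unmasked Study Coordinator will provide both the study hematologist and the GMP laboratory with information regarding which Treatment study visit will require" the real procedure and which the sham. The masking tables in both documents list the hematologist, the unmasked coordinator and the treating ophthalmologist as unmasked. When the treating ophthalmologist is told is not stated. SAP 3.3 says "Randomization will need to occur prior to the baseline visit for logistical and scheduling reasons", so time passes between assignment and Day 0.

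**The Day 0 check.** That morning "the participant will meet with the hematologist and the unmasked study coordinator to ensure there are no new contraindications to proceeding with study treatment". In addition, before the injection, "the unmasked treating ophthalmologist will perform a complete eye exam including fundus examination and a slit lamp examination of the study eye". No masked person is named in the decision, and no list of criteria is given for it.

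**The analysis set.** The modified ITT population "consists of all participants who were randomized and received the first injection (cellular or sham") (SAP 4.1.2; likewise Protocol 7.8.2.2 and SAP 7.3). Two rows of SAP Table 2 (section 3.6) matter:

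- Scenario 1: a participant who terminates or withdraws before Day 0 therapy is not in ITT, is followed only to close out adverse events, and is replaced. An inadequate aspirate is expressly included.
- Scenario 3: an inadequate aspirate in period 2 leaves the participant in ITT.

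At most one participant may be replaced (Protocol 7.6, SAP 3.6). SAP 11.0 lists the disposition and early-termination tables by arm for the ITT population only. No analysis of all randomized participants is planned.

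**The concern.** A modified ITT set is defensible when the decision not to treat cannot depend on the assignment. Here the people deciding know it, and the procedures differ: a real aspiration punctures bone, a sham punctures skin only. The same new finding could reasonably stop one and not the other.

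The inadequate-aspirate rule adds a second route that involves no judgment. It conditions the immediate-cell arm on adequate yield and places no such condition on the sham-first arm.

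At stake is the randomized comparison behind the month-6 efficacy analysis and the Period 1 comparison of adverse events. In the tables as listed, by-arm disposition would not show who was removed.

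**Working it through.** The plan states no figure for stops before the first injection, so there is none to reproduce. The check is mainly of the text.

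**Step 1. Order of events at Treatment 1**

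| Step | Who | Knows the arm? |
|---|---|---|
| Hematology consult, before randomization | Hematologist | No |
| Randomization | Unmasked coordinator | Yes, from here |
| Arm passed on | Hematologist, GMP laboratory | Yes |
| Morning check for new contraindications | Hematologist, unmasked coordinator | Yes |
| Eye examination before injection | Treating ophthalmologist | Listed as unmasked |
| First injection | – | Entry to the modified ITT set |

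The decision falls after disclosure and before entry to the analysis set.

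**Step 2. The same failure in each arm**

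| Inadequate aspirate | Immediate-cell arm | Deferred-cell arm |
|---|---|---|
| When it can occur | Treatment 1 | Treatment 2 |
| SAP Table 2 | Scenario 1: not in ITT | Scenario 3: in ITT |
| Month-6 visit | Not performed | Already done |

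**Step 3. How often.** SAP 3.2 gives 20 participants, 1:1, so 10 per arm; one exclusion is 1/10 = 10% of an arm. For an assumed stop rate q, the chance of at least one stop in an arm is 1 − (1 − q)^10:

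| q (assumed) | 2% | 5% | 10% | 20% |
|---|---|---|---|---|
| At least one stop | 18% | 40% | 65% | 89% |

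**Step 4. How much, under assumption.** SAP 13.1 gives SDs of 15 (participant) and 6.2 (measurement error), so the total SD = √(15² + 6.2²) = 16.23. With 10 per arm and two-sided alpha 0.05, t-test power at 20 letters is 74.1%, and 70% is reached at about 19.1 letters, which agrees with the SAP's description. Power at 20 letters is 71.5% with 9 against 10, and 68.4% with 8 against 10.

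- Simple case: if the excluded eye lies d letters below the other nine, the arm mean rises by d/10. With d = 15 (assumed), that is 1.5 letters. The standard error of the arm difference is 16.23 × √(2/10) = 7.26, so the shift is 1.5/7.26 = 0.21 standard errors.
- Deliberately unfavorable case: no true effect, and the eyes with the lowest baseline acuity dropped from one arm only (100,000 simulated trials).

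| Dropped from one arm | Shift in letter score | Rejection (nominal 5%) | Shift in change from baseline | Rejection |
|---|---|---|---|---|
| 1, not replaced | +2.35 | 6.8% | −0.41 | 5.1% |
| 1, replaced | +2.11 | 6.4% | −0.38 | 5.2% |
| 2, none replaced | +4.38 | 9.4% | −0.76 | 5.3% |
| 2, one replaced (the cap) | +3.88 | 8.9% | −0.68 | 5.4% |

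Replacement barely changes the shift. The sign differs between the two planned scales, so no direction of bias can be asserted.

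**The case against.** **The case for the plan.** The hematologist reviews history, medications and blood count before randomization, without knowing the arm, so only findings new since then are open to influence. Every participant is due a real aspiration by about month 6, which weakens any motive for leniency toward the sham-first arm. Efficacy is secondary: SAP 7.3 calls these analyses exploratory, and Protocol 7.8.2.2 bars using the p-values for hypothesis testing. A CONSORT diagram, a termination form giving the reason, and a record of unsuccessful aspirations are planned.

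**What stands.** These points limit the seriousness but do not close the route. The morning check exists to catch new findings, and neither an all-randomized analysis nor by-arm tables of uninjected participants are specified. It is also true that inadequate yield is a laboratory result, which later disclosure of the arm would not affect; that part needs follow-up and analysis.

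**Stronger readings the documents do not support:**

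- *Everyone stopped that morning is lost.* The check concerns that day. A participant who is deferred and later injected stays in the set.
- *Treatment 2 has the same effect.* The hematologist does review again beforehand, "to determine whether it would impact the outcome of the bone marrow aspiration procedure and continued treatment in the study". But those participants have had the first injection and stay in ITT, and the month-6 visit and Study Period 1 both precede Treatment 2.
- *The result is biased toward cells by a known amount.* Nothing in the documents links fitness for aspiration to visual outcome, and the letter shifts above rest on assumed selection.
- *Such exclusion happened.* The documents show a route only.

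**Conclusion.** The point holds for Treatment 1. Staff who know the arm can stop a participant before entry to the analysis set, and the inadequate-aspirate rule removes participants from the immediate-cell arm alone. Exclusion after randomization can therefore depend on arm.

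The firm figure is 10% of an arm per exclusion, given 10 per arm. Frequency is unknown: 18% to 89% for at least one stop in an arm, if the rate lies between 2% and 20%. The letter shifts are illustrations and are small beside a standard error of about 7.3 letters.

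Because efficacy is exploratory, this does not undermine the trial. It is worth correcting because the remedy is cheap and the loss would otherwise be hard to see.

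**What to change.** 1. **Timing of disclosure at Treatment 1.** Have the hematologist and treating ophthalmologist record the Day 0 fitness decision before the arm is released to them. The GMP laboratory and scheduling coordinator are still told at randomization, which meets the scheduling need in SAP 3.3. The coordinator will know the arm, so the recorded decision should be the physicians'. The clinical content of the check stays with the sponsor.
2. **Follow-up.** Amend SAP Table 2 scenario 1 so that randomized but uninjected participants are asked to attend the month-6 visit.
3. **Reporting and analysis.** Tabulate all randomized participants by arm, with the reason for any stop before the first injection. Add an all-randomized sensitivity analysis of the month-6 comparison by assigned arm. It should identify anyone who, after an inadequate yield, received the harvested cells in the open-label pilot study (Protocol 7.6). Include aspiration-related adverse events in uninjected participants in the safety tables: SAP 4.1.3 and 4.3 call for all consented participants, but SAP 11.0 lists those tables for ITT.

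**Cost.** Both specialists attend in either arm, so item 1 changes only when the assignment is released. Item 2 adds at most a few visits, and item 3 a few tables and one analysis. The documents do not say whether enrollment is complete; if it is, item 3 still applies with the data available.

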[#]Vital signs at Study Treatment 1 and Study Treatment 2 will be performed just before and after bone marrow or sham aspiration.

**For females of child-bearing potential (see APPENDIX B for definition), urine pregnancy testing should be done within 2 weeks prior to sham or cellular therapy.

[^]Using refraction previously obtained at Baseline visit.

[®]Study Treatment 1 and Study Treatment 2 eye examinations will be done before and after sham or cellular therapy.

***Includes full field and multifocal ERG.

^{@@} Includes research-grade ultra-high-resolution OCT and OCTA and adaptive optics-OCT in select patients who sign a separate consent. Advanced retinal imaging will be done on a separate day than the standard OCT/OCTA due to the time required for imaging. Imaging will be performed at baseline and participants with high quality images will have repeat imaging at 1 month after stem cell treatment, with at least 2 of the participants randomized to the deferred cellular therapy arm also having imaging after sham therapy. The images will be acquired and processed by unmasked investigators. Images will be masked prior to their review by a masked investigator and groups of images will be reviewed together to preserve masking.

^{##} For Immediate Cell Therapy/Deferred Sham Therapy group, study treatment at Day 0 consists of bone marrow aspiration followed by intravitreal injection of CD34+ cells, and study treatment at 6 months consists of sham bone marrow aspiration followed by sham injection. For Immediate Sham Therapy/Deferred Cell Therapy group, treatment at Day 0 consists of sham bone marrow aspiration followed by sham injection. For Immediate Sham Therapy/Deferred Cell Therapy group, treatment at Day 0 consists of sham bone marrow aspiration followed by sham injection, and study treatment at 6 months consists of bone marrow aspiration followed by intravitreal injection of CD34+ cells.

^{^^} The incorporation of the Exit Visit results from changes made to protocol v8.0 where follow-up was shortened to one year. For those participants who completed the Month 12 visit prior to the approval of protocol v8, they will complete the Exit Visit within 30 days of the approval of protocol v8.0. The Exit Visit is comprised of review and close-out of AEs and concomitant medication records, and completion of the study satisfaction survey.

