Fundus photography, fluorescein angiography, and autofluorescence will be performed at screening/baseline and at 3 months (±14 days) and 6 months (±30 days) after each treatment, and as needed at the discretion of the investigator to assess any significant change upon clinical examination. Commercial-grade OCT/OCT angiography, microperimetry and ERG will be performed at screening/baseline and at 1 month (±7 days), 3 months (±14 days) and 6 months (±30 days) after each treatment, or as needed at the discretion of the investigator to assess any significant change in retinal function and perfusion. The NEI VFQ questionnaire will be completed at screening/baseline and at 6 months following each study treatment. A study feedback questionnaire will be administered at 1 week after each study treatment and at study exit.

Select participants, who at screening have stable fixation on microperimetry and clear media (study eye) defined as Optovue OCTA signal strength of 6 or greater using the 3mm macular scan, will be invited to participate in an optional sub-study. The sub-study involves ultra-high-resolution OCT/OCTA and adaptive optics-OCT imaging. Imaging will be performed at baseline and participants with high quality images will have repeat imaging at 1 month after receipt of stem cell therapy. Approximately 2 of the participants randomized to immediate sham therapy/deferred cellular therapy will also have imaging done 1 month after receipt of sham therapy. Thus, the Advanced Retinal Imaging team will be unmasked investigators for the study duration. Since this is a time-consuming procedure, it may be scheduled on a separate date from other procedures requiring fixation, such as perimetry or ERG. The processed images will be evaluated for qualitative abnormalities by a masked investigator in bulk at a later date. The quantitative assessment of the images, e.g., retinal thickness and vascular density, will be assessed by the unmasked Advanced Retinal Imaging team after completion of image processing.

The schedule of assessments is presented in **TABLE 2**.

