The visual acuity examiners and photographers and technicians obtaining fundus photographs, fluorescein angiograms, OCT/OCTA and autofluorescence imaging, microperimetry and electroretinography (ERG) will be masked to study treatment assignment to avoid bias in outcome assessment. The advanced retinal imaging team, however, will be unmasked for the duration of the study.

Table 1: Masking of Treatment Assignment of EnrollmentCenter Personnel			
	Masked Status		
Principal Investigator	Masked		
Examining Ophthalmologist	Masked		
Masked Study Coordinator	Masked		
Hematologist	Unmasked		
Visual Acuity Examiner	Masked		
Treating Ophthalmologist	Unmasked		
Unmasked Study Coordinator	Unmasked		
Photographers	Masked		
OCT Technicians	Masked		
Perimetry Technicians	Masked		
ERG Technicians	Masked		
Study Participants	Masked		
Advanced Retinal Imaging Team	Unmasked		
GMP Laboratory Team	Unmasked		

All DCC staff will be unmasked to treatment assignment throughout a participant's follow-up. Knowledge of the treatment assignment by DCC staff will not affect assessment of therapy outcome as there will be little to no interaction of DCC staff with visual acuity examiners, examining ophthalmologists, study photographers or technicians, or study participants. Care will be taken when DCC staff are conversing with site personnel. DCC staff will be trained in the masked status of each site staff member especially the Study Coordinators to ensure that during regular communications information that may be unmasking is not inadvertently provided. The electronic data capture system will be designed in such a way that masked staff will not have access to any data related to therapy or adverse events reported during the first month following therapy as this information is potentially unmasking.

While the study is ongoing, site personnel, including the Study PI, will not have access to cumulative summaries of study findings broken down by treatment arm. Instead, these summaries will be presented only to the DSMC within a closed session in which only the DSMC members and select DCC staff (e.g., study statistician) are present. Although not fail-safe, restricting access in this way will help prevent unintentional changes in study implementation.

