7.4 Exploratory Outcomes

7.4.1 Advanced Retinal Imaging (Investigational OCT)

Advanced retinal imaging (ARI) will be performed in select participants who have consented and who, in the study eye at screening, have stable fixation on microperimetry and clear media defined as Optovue OCTA signal strength of 6 or greater using the 3mm macular scan. The ARI substudy involves adaptive optics-OCT imaging and ultra-high resolution OCT/OCTA. A table of the status of ARI acquisition, processing and review will be provided, along with a corresponding listing, to summarize how many participants were eligible for ARI and how many had images acquired, processed, and reviewed. A listing of advanced retinal imaging outcomes measures will be provided. Table 11 outlines the information that will be included in the outcome listing.

Table 11: Advanced Retinal Imaging Outcomes			
Modality	Outcome Measure ¹	Timepoints	
Adaptive Optics	Integrity of retinal vascular wall, inner and outer retinal layer and IS/OS	Baseline and 1 month following each treatment ²	
	Number of hyperreflective foci along vascular wall, inner and outer retina and vitreous	Baseline and 1 month following each treatment ²	
Ultra-high resolution	Total, inner, and outer retinal thickness and DRIL length	Baseline and 1 month following each treatment ²	
OCT/OCTA	IS/OS integrity	Baseline and 1 month following each treatment ²	
	Number of hyperreflective foci (vitreous, within retina, under retina)	Baseline and 1 month following each treatment ²	
	Superficial, intermediate, and deep plexus vascular density measurements	Baseline and 1 month following each treatment ²	
	Superficial, intermediate, and deep plexus integrity	Baseline and 1 month following each treatment ²	
	Number of microaneurysms, total area of telangiectasia, and total area of retinal neovascularization	Baseline and 1 month following each treatment ²	

¹ Information on the following four locations will be provided: central 3 mm, eccentric 1, eccentric 2, and eccentric 3.

² In the immediate cell/deferred sham arm, timepoints include baseline and 1 month following cellular therapy. In the immediate sham/deferred sham arm, timepoints include baseline, 1 month following sham therapy and 1 month following cellular therapy.

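### Quantitative reading of the advanced retinal images is left to the unmasked imaging team, although the protocol already provides for masked, grouped review of the same images

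*Protocol*

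**What the plan says.** Protocol 6.1.5 divides the reading of the research-grade OCT/OCTA and adaptive optics images between two parties. For qualitative features: "The processed images will be evaluated for qualitative abnormalities by a masked investigator in bulk at a later date". The quantitative assessment, with thickness and vascular density as the examples given, "will be assessed by the unmasked Advanced Retinal Imaging team after completion of image processing".

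The Table 2 footnotes in the same section add two facts. On acquisition and processing: "The images will be acquired and processed by unmasked investigators". On review: "Images will be masked prior to their review by a masked investigator and groups of images will be reviewed together to preserve masking". That footnote does not limit the masked review to qualitative features; only the body text of 6.1.5 does.

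The team's status is openly stated. Protocol 6.1.2 says "The advanced retinal imaging team (described in Section 6.1.5), however, will be unmasked for the duration of the study", SAP 3.4.2 says "The advanced retinal imaging team, however, will be unmasked for the duration of the study", and the masking table in each document agrees. Protocol 6.2 names the team as an exception to masked outcome assessment.

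SAP 7.4.1, Table 11, lists the measures, for example "Superficial, intermediate, and deep plexus vascular density measurements", at four retinal locations. It does not say who reads any of them.

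**The concern.** The people who measure thickness and vascular density know which scans are baseline and which follow cell therapy. If placing a boundary, accepting a segmentation or setting a threshold needs judgement, that knowledge can move the values in the hoped-for direction. The main contrast in the sub-study is baseline against one month after cells in the same eye, so such a shift would look like a treatment effect.

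The data have a use beyond the listing. Protocol 7.8.2.3 plans an analysis of change from baseline in vascular density and morphology, and Protocol 7.8.3 hopes for trends in morphology or perfusion that would support a larger trial. A trend read by people who knew the visit would carry less weight in that argument.

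**Working it through.** No arithmetic yields a bias estimate here. The check sets the provisions side by side.

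1. **Reason for unmasking.** Protocol 6.1.5 presents the team's unmasked status as a consequence of the schedule: repeat imaging follows cell therapy, and only a few deferred-cell participants are also imaged after sham. Whoever books and acquires the scans can infer the treatment. This does not carry over to measuring stored, processed images, from which the labels can be removed. Neither document gives another reason.

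2. **Masking step.** The Table 2 footnote provides for images to be masked and reviewed in groups by a masked investigator, so the procedure exists in the plan. The order in time is not fixed. The masked review comes later, and quantification follows processing, so the masked sets may not exist when the measurements are made.

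3. **Which measures are affected.** Table 11 has eight rows.
   - Two contain a measure named in 6.1.5: the row with retinal thickness (which also holds DRIL length) and the plexus vascular density row.
   - Three concern integrity (vascular wall and layers, IS/OS, plexus) and fit the qualitative review.
   - Three are counts or areas: foci on adaptive optics, foci on OCT/OCTA, and microaneurysms with areas of telangiectasia and neovascularization.

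   Check: 2 + 3 + 3 = 8. Only thickness and vascular density are expressly given to the unmasked team. DRIL length, the counts and the areas are not assigned to a reader.

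4. **Automation.** Commercial OCTA vascular density is labelled automated in Protocol Table 3 and SAP Table 5. Table 11 uses no such label, and neither document says how the research-grade measurements are made or whether a masked reader repeats them.

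5. **Control images.** Protocol 6.1.5 plans post-sham imaging in about two deferred-cell participants. The synopses and the Table 2 footnote say at least two. The Table 11 footnote lists a post-sham time point for that arm without a number. With 20 participants randomized 1:1, the arm has about 20 / 2 = 10 members. At the planned minimum of two, a drift in reading could hardly be told from a cell effect.

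6. **Reach.** Protocol 6.3.3 classes these outcomes as exploratory. SAP 7.4.1 plans a status table and listings, with no test and no between-arm estimate.

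**The case against.** The strongest reply is that this is a disclosed choice about outcomes on which little depends. Protocol 6.2 makes the exception explicitly, the sub-study is optional, and the SAP draws no inference from it. That stands, and it sets the weight of the point.

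A second reply is that the mechanism is assumed. If thickness and density come from fully automated software, reader bias on those measures would be small. This also stands, which is why the point is conditional on judgement entering the measurement.

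A third reply is that coding is an imperfect remedy. Processing is done unmasked and stays so, and a team that scanned a small number of eyes may recognise them. The documents show the masked investigator in a qualitative role only, so his or her ability to quantify research-grade images is not established. All of this is correct. It limits the gain but does not remove it.

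Three stronger readings are tempting and are not supported:
- **That the masking provisions contradict each other.** They do not; the exception is stated wherever it matters.
- **That every count and area in Table 11 is read unmasked.** The documents do not assign those rows, and some could be recorded at the masked review.
- **That the trial's OCT results in general are read unmasked.** The provision covers research-grade images only. The commercial OCT/OCTA used for the secondary outcomes is obtained by masked technicians.

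The scarcity of post-sham images would exist whoever read them. It matters here only because it leaves little against which to detect drift.

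**Conclusion.** The point holds as a modest design improvement. The protocol gives thickness and vascular density to unmasked readers for a reason that applies to acquisition, while already providing for masked, grouped review of the same images. The risk is to exploratory, listing-only changes from baseline to post-cell imaging. The primary safety and feasibility outcomes and the secondary efficacy outcomes are untouched.

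The size of the bias cannot be computed. The conclusion assumes that at least some of the measurement involves judgement, which the documents neither state nor exclude. If a measure is fully automated, and the SAP says so, the concern about its reader falls away.

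**What to change.** Amend Protocol 6.1.5 so that any quantitative measurement involving reader judgement is made on images with participant, arm and visit labels removed and the order shuffled, using the masking step in the Table 2 footnote. Lock the values before they are linked to arm and visit. The masked investigator should make the measurements where able, since that reader did not acquire the scans; otherwise the imaging team should make them on the coded images.

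In SAP 7.4.1, state for each Table 11 measure who reads it, under what masking, and whether it is automated.

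The cost is a change of wording and of workflow order, with no new procedure for participants. Quantification has to wait until the images are coded. Unmasked choices during image processing remain, and the imaging team may still recognise some eyes.
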